7.5 Data Safety and Monitoring Board

The Data and Safety Monitoring Board (DSMB) will monitor the MIST trial. The DSMB will act in an advisory capacity to the study PIs to monitor participant safety, data quality and evaluate the progress of the studies being conducted.

The DSMB is responsible for ensuring subject safety (by reviewing blinded and unblinded safety data on a regular basis and assessing the safety of study procedures) and for monitoring the overall conduct of the studies. The DSMB will monitor enrollment, follow up and adverse events.

The DSMB is an independent group advisory to the PI and study team, and is required to provide recommendations about conduct of the trial. In addition, the DSMB is asked to make recommendations, as appropriate, about:

- Benefit/risk ratio of procedures and participant burden
- Selection, recruitment, and retention of participants
- Protocol violations and adherence to protocol requirements
- Completeness, quality, and analysis of measurements
- Amendments to the study protocol and consent forms
- Participant safety
- Notification of and referral for abnormal findings

The DSMB will consist of 3 members and strong consideration will be given to include at least one investigator with expertise in smoking cessation, 1 statistician, and 1 investigator with expertise in clinical trials. The DSMB will meet twice during the course of the study, which will be scheduled after approximately one third and approximately two thirds of the target number of participants have reached the final outcome. The DSMB has the authority to assess the option of stopping early for overwhelming benefit demonstrated in the primary study endpoint, or for safety concerns. The panel will make recommendations about the continuation, modification, or termination of the study to the study steering committee. Unscheduled meetings can be requested by any party with the responsibility of overseeing the study.

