5.8 Randomization

Patients can be randomized into the study once the NMR test has resulted. Randomization will be stratified on three factors: (1) primary admitting diagnosis (cardiac vs. other); (2) cigarettes/day (≥10, <10); (3) primary insurance (Medicaid, Medicare with Part D, Private Insurance, Federal/Other Governmental/Other Insurance); and (4) NMR status ("normal"/"slow") to ensure that the treatment groups are balanced. After the patient enrolls, the RA will be directed to the electronic randomization screen in REDCap, which, once submitted, automatically assigns the participant to a randomization group.

Blinding: The nature of the study precludes blinding of patients or research staff to the study condition.

Participants will receive a handout describing their assigned treatment. For those randomized to the MIST (precision) arm, the handout will include information on the NMR result and recommended medication. In the event that a participant is enrolled before a valid NMR result is received, study staff may contact the participant via phone/text/email (per participant preference) to notify of randomization status and initiate post-randomization procedures including facilitation of smoking cessation medication. Those randomized to the Usual Care arm will receive their NMR result at study completion, 12 months post-study enrollment; participants in the Usual Care arm who withdraw from the study will not be provided precision care information.

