9.0 Statistical Considerations

9.1 Aim 1

The primary study outcome is biochemically-verified self-reported 7-day point prevalence abstinence at 6 months as defined by salivary cotinine level < 10 ng/ml or expired CO <10 ppm. A secondary outcome is biochemically-verified self-reported 7-day point prevalence abstinence at 12 months. Brief surveys will be conducted at 6 and 12 months after study enrollment to determine self-reported abstinence. Biochemical validation of smoking status is accomplished via mailed salivary cotinine samples or expired CO.

Analysis:

The effect of MIST vs. UC on biochemically-verified abstinence at 6 months will be estimated via a relative risk of abstinence and tested at a 5% significance level via a chi-squared test with Yates' continuity correction. The same method will be applied

to the secondary outcome at 12 months. Anticipated loss to follow up is accounted for in the expected approximate UC abstinence rates where persons lost to follow up will be treated as non-abstinent. However, sensitivity analyses will consider a range of possible odds ratios (1, 2, and 5) linking loss to follow-up and smoking. [51] Exploratory analyses testing for effect heterogeneity will use multivariate logistic regression models adjusting for the main effect of a potential modifier and testing for an interaction with the effect of MIST. The potential effect modifiers to be explored are age, race, sex, NMR, and pre-intervention plan to quit.

Power:

Conservatively assuming a biochemically validated abstinence rate of 10% under UC, a chi-squared test on 1000 patients (at 6 months) will detect a MIST abstinence rate of 16.2% (Risk Difference=6.2%, Relative Risk=1.62, Odds Ratio=1.74) with 80% power. Assuming a 15% biochemically validated abstinence rate under UC (at 12 months), a 22.2% rate under MIST (RD=7.2%, RR=1.48, OR=1.62) is detectable with 80% power. Power was estimated via simulating 20K datasets under the settings above in the statistical program R and were checked against the simplified estimates of the pwr package.

9.2 Aim 2

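### Does leaving the DSMB's early-benefit threshold unstated put the 5% error of the primary test at risk?

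*Combined protocol and SAP*

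**What the plan says.** Section 7.5 schedules two DSMB meetings, after "approximately one third and approximately two thirds of the target number of participants have reached the final outcome". It describes the routine remit as follows: "The DSMB will monitor enrollment, follow up and adverse events". It then adds an efficacy option: "The DSMB has the authority to assess the option of stopping early for overwhelming benefit demonstrated in the primary study endpoint". The board recommends to a steering committee and does not itself end the trial. Strong consideration is to be given to seating a statistician among its three members. Section 7.5 also provides that "Unscheduled meetings can be requested by any party with the responsibility of overseeing the study".

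Section 9.1 defines the endpoint: "The primary study outcome is biochemically-verified self-reported 7-day point prevalence abstinence at 6 months". The effect of MIST against usual care (UC) is "tested at a 5% significance level via a chi-squared test with Yates' continuity correction". The power statement begins "Conservatively assuming a biochemically validated abstinence rate of 10% under UC" and gives 80% power against 16.2% with 1000 patients. Section 9 mentions no interim look, boundary or adjusted final level, and the documents cite no DSMB charter.

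**The concern.** If a board may stop for benefit at either of two looks and the final test still uses the full 5%, there are three chances to declare success. How far the error then exceeds the nominal level depends on the interim threshold, which the plan does not state. A number set after unblinded results had been seen would not be prespecified, and the trial's main claim could be challenged.

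Two loose ends add to the doubt. The trigger in 7.5 could mean the 6-month primary endpoint or the 12-month visit, since 5.8 speaks of UC participants getting their result "at study completion, 12 months post-study enrollment". In addition, 7.5 does not say whether an unscheduled meeting may look at efficacy.

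**Working it through.** **Inputs.** From 9.1: N = 1000, UC 10%, MIST 16.2%, Yates chi-squared, 5%. From 7.5: looks at about 1/3 and 2/3. Assumed: 1:1 allocation, so looks at 167, 333 and 500 per arm; interim stopping only for benefit; final two-sided test at 0.05.

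**Test statistic.** With n per arm and pooled rate p̄, Z = (|p_M − p_U| − 1/n) / √(2·p̄(1 − p̄)/n).

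**Plan's own figure.** The continuity-corrected sample-size formula for 10% vs 16.2% gives 496 per arm (992 in total). Exact enumeration at 500 per arm gives power of 80.8%. The stated 80% with 1000 patients is reproduced, for a single final test.

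**Type I error.** Start from the product of two Binomial(167, p) distributions. Remove the outcomes with Z at or above the interim critical value and add their probability to the error. Convolve the rest with 166 further patients per arm and repeat. Convolve with the last 167 per arm and add the probability that |Z| ≥ 1.96. No simulation is involved. The 15% rate is the plan's UC figure for 12 months, used here only as a sensitivity value.

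| Interim threshold at both looks | Overall error, 10% (15%) | False benefit for MIST, 10% (15%) |
|---|---|---|
| none (single final test) | 3.84% (4.06%) | 1.9% (2.0%) |
| p<0.001 | 3.85% (4.08%) | 1.9% (2.0%) |
| O'Brien-Fleming interim levels (0.0005, 0.014), final left at 0.05 | 4.0% (4.2%) | 2.1% (2.2%) |
| p<0.01 | 4.1% (4.3%) | 2.2% (2.3%) |
| p<0.02 | 4.5% (4.7%) | 2.6% (2.7%) |
| p<0.03 | 4.9% (5.2%) | 3.0% (3.1%) |
| p<0.05 | 5.8% (6.2%) | 3.9% (4.2%) |

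For the 10% rate, the parts (look 1 + look 2 + final) are:
- p<0.001: 0.02% + 0.03% + 3.81%, total 3.85% after rounding.
- p<0.05: 1.57% + 1.32% + 2.93% = 5.82%.

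Overall error passes 5% only for thresholds looser than about p<0.032 (p<0.026 at 15%). False benefit passes 2.5% for thresholds looser than about p<0.019 (p<0.015).

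**What each threshold means in counts.** Suppose UC has 17/167 abstinent (10.2%) at the first look.
- p<0.05 needs 31/167 on MIST.
- p<0.02 needs 34/167: Z = (0.1018 − 0.0060)/0.0394 = 2.43, p = 0.015.
- p<0.001 needs 41/167: Z = (0.1437 − 0.0060)/0.0415 = 3.32, p = 0.0009.

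**The loose ends.**
- *Trigger read as 12 months.* Assume uniform accrual over 60 or 24 months (not in the documents). Six more months of accrual add 500 × 6/60 = 50 or 500 × 6/24 = 125 per arm, so the looks fall at 217/383 or 292/458. At p<0.001 the error is 3.85% or 3.84%; at p<0.05 it is 5.7% or 5.3%.
- *One extra efficacy look at 250 per arm.* The error is 3.86% at p<0.001 and 6.3% at p<0.05.

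**Effect of writing a rule in.** Power at 10% vs 16.2% is 80.8% with no looks, 80.8% with p<0.001 and final 0.05, 80.6% with final 0.0495, and 79.9% with a full O'Brien-Fleming boundary.

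**The case for a change.** The strongest opposing case is that a word is not a rule. No boundary or charter is cited, so the threshold could be settled after the board has seen data. That the board only advises does not help: acting on its advice has the same error consequences. The room below 5% is a by-product of the Yates correction. With an uncorrected chi-squared test and benefit-only stopping, normal theory gives 5.03% at p<0.001 and 5.4% at p<0.01. If either direction could stop the trial, the Yates test reaches 5.1% already at p<0.02. Judged by false claims of benefit against 2.5%, the margin also ends sooner, near p<0.019.

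The threshold affects more than error. At the design effect, the chance of crossing at one of the two looks is about 15% at p<0.001 (3.3% + 12.0%), 50% at p<0.02 (21.0% + 28.9%) and 65% at p<0.05 (33.4% + 31.8%). Early stopping could also thin the 12-month data.

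It stands that the number is unwritten and that it governs how likely the trial is to stop early. It does not follow that the primary inference is unsafe. The text sets the bar at an overwhelming result, not merely a significant one, and a board would ordinarily turn that into p<0.001, O'Brien-Fleming levels or p<0.01. All three stay below 5% overall and below 2.5% for false benefit, at both rates. The Yates correction is the test that 9.1 prescribes, so its conservatism belongs to the plan. Nothing in the documents shows that the threshold would in fact be picked after seeing results; the board can fix it before its first look.

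**Conclusion.** No change to the plan follows. The threshold is a missing detail, and its ordinary readings give a sound result: overall error of 3.85% to 4.1% at the 10% planning rate (4.1% to 4.3% at 15%), against 3.84% (4.06%) for the single test. Exceeding 5% would require a board to treat an interim p-value of about 0.03 or more as overwhelming, and even at p<0.05 the figure is 5.8% (6.2%). Putting the usual strict threshold into the text would leave the final test at 0.05, the sample size at 1000 and power at 80.8%. The trigger's wording and the possibility of an unscheduled look do not alter this under a strict threshold.

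The conclusion rests on 1:1 allocation, looks near one third and two thirds, interim stopping for benefit only, and use of the Yates test at every look. Two-sided interim stopping gives 3.9% at p<0.001 and 4.3% at p<0.01 for the 10% rate, so the conclusion does not depend on the benefit-only assumption.

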8.0 Study Withdrawal/Discontinuation

Study withdrawal: A participant can voluntarily withdraw from the study at any point in time throughout the course of the study. The participant will not be penalized in any way for voluntarily withdrawing from the study. To withdraw, the patient will be asked to inform the research team in writing of their intent to withdraw including their reason for leaving the study. Participants who withdraw from the study will no longer be eligible for compensation for any study procedure that was not completed prior to withdrawal. If, during the enrollment and randomization process, or shortly thereafter, it comes to the attention of the study staff that a participant has become ineligible (e.g., patient's medical condition deteriorates while in hospital such that they are now too ill to participate; patient develops a medical condition that makes them ineligible to use smoking cessation medication, etc.), then the team would cease the enrollment process and/or administratively withdraw the participant.

Medication discontinuation: Participants who choose on their own to discontinue medication may do so. Other conditions may prompt study staff to recommend medication discontinuation. For example, pregnancy and lactation are exclusion criteria for the study. If during the study a participant informs study staff of a pregnancy, the participant will be asked to discontinue study medication and to visit the PCP for a confirmatory pregnancy test. Other conditions that would prompt study staff to recommend discontinuation of medication include side effects that could not be managed with usual good clinical practice. All participants who discontinue their medication for any reason will be followed and analyzed by intention to treat.

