Aim 1: Biochemical Verification of Self-Reported Abstinence (Table 2, Row 1) For participants who self-report abstinence at the 6 month and/or 12 month follow up surveys, study staff will attempt to biochemically-verify the self-report. Based on prior experience with challenges in obtaining biochemical verification, there will be several options including: (1) saliva cotinine (in- person or mailed); (2) end-expired carbon monoxide (in-person or remote) if participants are unwilling or unable to verify with cotinine (e.g., actively using NRT). Standard saliva cotinine kits will be analyzed by Salimetrics Laboratory or other comparable lab. Smoking abstinence can also be confirmed through in-person or remote carbon monoxide (CO) testing (if a participant is on NRT). If a participant is unable to complete an in-person CO, then a personal CO device (such as a CoVita iCO Smokerlyzer) may be mailed to the participant to complete the CO reading remotely. We have successfully used this protocol for mailed cotinine samples and CO testing in the past. Smoking abstinence will be defined conservatively according to recommended standards. The following cessation milestones will be assessed in addition to point prevalence abstinence (PPA):

- i. *Initial abstinence* is defined as the first instance in which the participant refrains from smoking for at least 24 hours; duration of initial abstinence will also be assessed.
- ii. *Initial lapse,* defined as the first episode of ANY smoking, even a puff, after achieving initial abstinence, will also be assessed.
- iii. Continuous abstinence is defined as no smoking, even a puff, since study enrollment (i.e., achieved PPA at 1, 3, 6, and 12 mo +no smoking in between surveys + biochemical validation of selfreported (SR) PPA at 6, 12 mo). Participants who are unable to biochemically verify abstinence will be assumed to be smoking, by convention, but sensitivity analyses will consider a range of possible odds ratios (1, 2, and 5) linking loss to follow-up and smoking. [51]

| Table 2: Main Ou | itcome Measures by Study | y Aim | | | | |
|-----------------------------------|--|--------------|---|--|--|--|
| Outcome | Measure | Data sources | | | | |
| | | Survey | Other source | | | |
| AIM 1: | SR at 1, 3, 6, 12 m | | | | | |
| Abstinence | Biochem. validation at 6 m (primary study | Х | 12 m* via saliva cotinine <10 ng/ml or expired CO <10ppm | | | |
| AIM 2. | SR at 1 3 6 12 m | | | | | |

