- a. This composite clinical outcome will be assessed by passive query of the VUMC EHR, the Tennessee Medicaid (TennCare) database, and the Department of Health Hospital Discharge Data System. The composite variable includes any evidence of a documented incident inpatient hospitalization, ER visit, or death during the follow up period. Death will be defined as death due to any cause as determined by National Death Index or death certificate data from Tennessee State Vital Record Files. Cause-specific mortality will be determined via death certificates obtained from the Tennessee State Vital Records, which has death certificates for all deaths in Tennessee and for Tennessee residents who die in adjoining states. Passive surveillance of 12-month clinical composite outcomes takes place at VUMC and non-VUMC facilities, as described further below.
 - i. At VUMC facilities. Hospitalization and ER visits at VUMC are tracked by Drs. [name] and [name], leveraging VCREATE and V-SERCH Center resources including validated EHR algorithms to extract clinical outcomes including ER visits, hospitalizations and mortality.
 - ii. At non-VUMC facilities. We have established links between VUMC EHR data and external databases including Tennessee Medicaid and the Hospital Discharge Data System (TN-HDDS). The TN-HDDS collects patient-level discharge information in visits from all hospitals licensed by the Tennessee Department of Health (TN DOH), including rehabilitation hospitals, psychiatric units within acute care hospitals, and free-standing ambulatory surgical treatment centers. Tennessee Medicaid (TennCare) maintains an extensive electronic data system and records of all their healthcare encounters, including pharmacy prescriptions filled.
- b. Vital status may be ascertained by study staff reviewing VUMC medical records, utilizing automated electronic health record (EHR) deceased notifications, conducting obituary searches, participant proxy contacts, and PCP/provider offices. Death certificate data from the Tennessee Office of Vital Records may also be used to identify all deaths occurring within Tennessee, and deaths of Tennessee residents that occur in surrounding states. Vanderbilt's Health Policy Department processes these data for research and public health surveillance activities via data use agreements with the TN DOH. Finally, data from the National Death Index or related databases that include information on mortality may be queried.

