A secondary outcome is participant self-reported medication adherence assessed at the 1- and 3-month surveys (Aim 2a). Another secondary outcome is PCP prescriptions for smoking cessation medication after study enrollment for participants who continue to smoke. Pharmacy data from CMS will also be used to supplement participant's self-report of whether they received smoking cessation medication prescriptions from their PCP after study enrollment (Aim 2b) and whether the prescriptions were matched to NMR (Aim 2c).

Analysis:

To account for the longitudinal structure of the data with observations at months 1, 3, 6, and 12, Aim 2 analyses will utilize general estimating equations (GEE) with an autoregressive (AR1) correlation structure adjusting for self-reported smoking status and age, race/ethnicity, education, and dependence (baseline FTND score) in a multivariate logistic GEE model. Each of the following three models will estimate a common odds ratio for MIST vs UC for the outcome of interest. All patients will be included in the analyses and missing covariate data will be multiply imputed via predictive mean matching imputation. Standard errors will be estimated via Rubin's rules and statistical significance tested via Wald tests. Unobserved adherence status or prescriptions will be treated as non-adherent or not received, respectively. H2a: We will estimate the odds ratio for being adherent in the 3 months post-enrollment. H2b: We will estimate the odds ratio for receiving a PCP prescription for a smoking cessation medication in the 12 months post-enrollment. PCP prescriptions occurring between any two time points, e.g. months 3 and 6, will be attributed to the latter time point for analysis. H2c: We will estimate the odds ratio for receiving an NMR-

matching PCP prescription. Exploratory and sensitivity analyses: For each of the three outcomes, exploratory analyses will test for interactions between the MIST effect and month of follow up; and for interactions between the MIST effect and medication type (NRT or varenicline). Sensitivity analyses will vary the correlation structure assumptions to ensure the main conclusions are robust to model specifications.

Power:

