The composite health care and mortality outcomes are gathered via VUMC EHR, state vital records, and the existing Tennessee HDDS, thus patients are presumed to not have an event unless one is observed. Conservatively assuming a composite outcome rate of 50% under UC (which is based on EHR estimates from VUMC smokers in care), a Chi-squared test will detect a MIST rate of 41.0% (RD=-9.0%, RR=0.82, OR=0.70) with 80% power. Assuming rates for UC of 10%, 20%, and 30% respectively for mortality, ED visits, and hospitalizations, a Chi-squared test on 1000 patients will detect with 80% power MIST rates of, respectively, 5.1%, 13.2%, and 22.0% (RD=-4.9%, -6.8%, 8.0%; RR=0.51, 0.66, 0.73; OR=0.48, 0.61, 0.66).

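### Does the administrative-withdrawal rule in section 8.0 leave the Aim 1 and Aim 3 denominators open?

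*Combined protocol and SAP*

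**What the plan says.** Section 8.0 has two paragraphs. The first, on leaving the study, covers ineligibility that comes to light "during the enrollment and randomization process, or shortly thereafter". Its examples are a patient who becomes too ill and one who develops a condition that rules out cessation medication. In those cases "then the team would cease the enrollment process and/or administratively withdraw the participant". The second paragraph, on stopping medication, ends: "All participants who discontinue their medication for any reason will be followed and analyzed by intention to treat".

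The outcome rules are elsewhere:

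- **Aim 1.** Section 5.9, in the item on continuous abstinence: "Participants who are unable to biochemically verify abstinence will be assumed to be smoking, by convention". Section 9.1 says that expected loss is already built into the assumed usual-care (UC) rate, in that "persons lost to follow up will be treated as non-abstinent". It bases power on 1000 patients, the approximate enrolment given in section 2.1.
- **Aim 2.** Section 9.2: "All patients will be included in the analyses".
- **Aim 3.** Section 9.3 names its sources as the EHR, vital records and the state discharge system, "thus patients are presumed to not have an event unless one is observed". Section 5.9 describes the method: "This composite clinical outcome will be assessed by passive query of the VUMC EHR" and of external databases.

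Section 5.8 says that neither patients nor research staff are blinded.

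**The concern.** Three things make this look like a flaw. First, the withdrawal rule extends a little past randomisation, its grounds can be prognostic, and the staff who apply it know the arm. Second, the plan's only intention-to-treat sentence is about people who stop medication, not people withdrawn from the study. Section 9.2 says all patients are included, whereas 9.1 and 9.3 have no matching sentence. Third, someone who starts medication, develops a condition that rules it out and stops it falls under both paragraphs of 8.0: withdrawn by one, followed and analysed by the other.

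If withdrawn participants were dropped, and more came from one arm, the randomised comparison would be lost for them. Abstinence would be overstated in the arm that lost more. For Aim 3, the sickest participants would disappear from that arm; or, if surveillance stopped for them, their later events would be recorded as no event.

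**Working it through.** **1. Reading the text.** The withdrawal sentence ends a person's participation. It does not say that their outcome is removed from analysis. What happens to a missing outcome is settled by the Aim 1 rules: unverified counts as smoking, and lost counts as non-abstinent. Section 9.1 does not inflate the sample for attrition, because loss is absorbed in the assumed abstinence rate. That works only if people without an outcome stay in the denominator. Section 9.3 does the same by presuming no event. Passive database queries need no contact with the participant, and no sentence stops them on administrative withdrawal. Section 4.0 places randomisation after all criteria are confirmed, so the rule's reach past that point is short.

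**2. The plan's own figure.** Inputs from 9.1: 1000 patients, UC 10%, MIST 16.2%, chi-squared test with Yates' correction at 5%. Allocation of 500 per arm is an assumption, since no ratio is stated. The method sums binomial probabilities over all pairs of counts for which the corrected statistic exceeds the 5% critical value. Power is 80.8%, which reproduces the stated 80%. With 10% in both arms the rejection rate is 3.84%, of which 1.92% favours MIST.

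**3. Effect of dropping or keeping.** The plan gives no withdrawal rate. Assume k withdrawn per affected arm, none of them abstinent, with the stated rates holding among all randomised. If k are dropped from an arm, its apparent rate is 50/(500 − k) when the true rate is 10%, and 81/(500 − k) when it is 16.2%.

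| Scenario | k = 10 | k = 15 | k = 25 |
|---|---|---|---|
| Kept as non-abstinent: null rejection | 3.8% | 3.8% | 3.8% |
| Kept as non-abstinent: power | 80.8% | 80.9% | 80.9% |
| Dropped equally: null rejection | 3.9% | 3.9% | 3.9% |
| Dropped equally: power | 80.8% | 80.9% | 81.1% |
| 2k dropped, split 60:40 (more from MIST): RR under no effect | 1.01 | 1.01 | 1.02 |
| MIST only dropped: RR under no effect | 1.02 | 1.03 | 1.05 |
| MIST only dropped: null rejection | 4.0% | 4.1% | 4.6% |
| MIST only dropped: power | 84.0% | 85.6% | 88.3% |
| UC only dropped: power | 77.1% | 75.2% | 71.0% |

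With equal removal, or with everyone kept, the RR under no effect is 1.00. For the 60:40 split it is (500 − 0.8k)/(500 − 1.2k); at k = 25 that is 480/470 = 1.02, with null rejection of 4.0%. With 25 dropped from MIST only, the share of null rejections favouring MIST rises from 1.9% to 3.6%. With 50 dropped from MIST only, the RR is (50/450)/0.10 = 1.11 and null rejection is 7.0%.

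**4. Cost of keeping them.** If the withdrawn came on top of the loss already in the planned rates, both rates shrink by (500 − k)/500. Power is then 79.8%, 79.3% or 78.3% for k = 10, 15 or 25. This overstates the cost, because the 10% already allows for loss.

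**5. Aim 3.** For mortality, take UC 10% from section 9.3, no true effect, and assume that 25 are withdrawn from MIST only and half of them die.

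- Dropped: [(50 − 12.5)/475]/0.10 = 0.79.
- Kept, but surveillance stops: [(50 − 12.5)/500]/0.10 = 0.75.
- Surveillance continues, or removal is equal by arm: 1.00.

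The first two figures need an assumed count, a one-arm pattern, an assumed death risk and an exclusion, or a stop to surveillance, that the plan does not prescribe.

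**The case for a change.** The best case for a change is that the missing-outcome rules say how to classify people in the denominator, not who belongs in it, and none of them names withdrawn participants. Two analysts could then defend different denominators for the primary test. A borderline result could turn on the choice: 70/500 against 50/500 gives p = 0.0645, and dropping ten non-abstinent MIST participants (70/490) gives p = 0.049. Writing the policy down would cost a few sentences.

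Part of this stands. The policy is not stated, and for the narrow group who stop medication and are also withdrawn, 8.0 is in tension with itself over whether they are followed. Over whether they are analysed it is ambiguous, not contradictory, since the withdrawal paragraph is silent on data.

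The rest is weaker. The analyst who drops people has no sentence to rely on, while the one who keeps them has the 1000-patient basis and the loss rule. The contrast with Aim 2 is also slight, because the sentence in 9.2 mentions neither withdrawn participants nor assigned arm. The borderline example needs all ten exclusions in one arm. Section 5.3 requires everyone to be medically eligible for both varenicline and nicotine replacement, so the plan gives no reason to expect that.

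**Conclusion.** The concern does not call for a change. The gap is real but is one of wording: the plan's sample-size basis and missing-outcome rules lead an analyst to keep every randomised participant, as non-abstinent for Aim 1 and with no event unless one is observed for Aim 3. On that reading Aim 1 is sound, with null rejection of 3.8% and power of about 81%.

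Even if withdrawn participants were dropped, equal removal does nothing and a 60:40 split of up to 50 moves the RR by at most 0.02. Null rejection stays under 5% with 25 of 500 lost from one arm only, though the bias in direction and power is then visible, and it reaches 7.0% with 50. These are limits for the assumed counts, not general bounds. The larger Aim 3 distortions belong to an exploratory aim that section 2.1 makes conditional on feasibility.

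The conclusion rests on 1:1 allocation, on withdrawn participants being non-abstinent, and on withdrawals being few and not strongly tied to arm. The plan gives no figure for the last of these.
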